17.2.7 Amended protocol 07: 21 January 2020

This amended protocol (amendment 07) is considered to be nonsubstantial based on the criteria set forth in Article 10(a) of Directive 2001/20/EC of the European Parliament and the Council of the European Union because it neither significantly impacts the safety or physical/mental integrity of participants nor the scientific value of the study.

Overall Rationale for the Amendment

The overall rationale for this amendment is as follows:

- To clarify that study duration for each patient is initially 6 years to align protocol wording with other study documents (ICF in particular) and align between different sections of the protocol.
- To modify the wording on duration of the additional follow-up period after the 6-year study for patients in the UK and Germany as follows: the duration of the additional follow up period will be up to the approval in the country or limited to a maximum of 2 years, whichever occurs first (ie, for UK and German patients, the total study duration per patient is 8 years at the maximum including the initial 6-year and the additional 2-year follow-up).
- To correct typographical errors in the table footnote references in Section 1.2.3.

Protocol amendment summary of changes table

Section # and Name	Description of Change	Brief Rationale
PROTOCOL AMENDMENT SUMMARY OF CHANGES TABLE	Document formatting revision	To update document history and provide overall rationale for the amendment
Clinical trial summary (Duration of study)	Clarification that study duration for each patient is initially 6 years. Revised wording for study follow-up period duration specific for the UK and German patients.	To align protocol wording with other study documents (ICF in particular) and align between different sections of the protocol. To comply with the UK and German Health Authority position regarding the protocol language with regards to study follow-up period duration.

Section # and Name	Description of Change	Brief Rationale
1.1 Graphical study design	Revised wording for study follow-up period duration specific for the UK and German patients.	To comply with the UK and German Health Authority position regarding the protocol language with regards to study follow-up period duration.
1.2 Study flow chart	Deleted specifics regarding neutralizing antibody testing. Corrected footnote references.	Details are provided in Section 9.1.7 Immunogenicity. To correct typographical errors in the study flow chart for the additional follow-up period.
6.2.1 Duration of study participation for each patient	Clarification that study duration for each patient is initially 6 years. Revised wording for study follow-up period duration specific for the UK and German patients.	To align protocol wording with other study documents (ICF in particular) and align between different sections of the protocol. To comply with the UK and German Health Authority position regarding the protocol language with regards to study follow-up period duration.
9.1.7 Immunogenicity	Corrected typographical error regarding antibody testing. Modified wording regarding the type of testing for neutralizing antibodies to avalglucosidase alfa Modified wording regarding duration of testing for anti-alglucosidase alfa IgG antibodies.	To specify testing to be done for anti-avalglucosidase alfa antibodies. To allow flexibility in case approval is obtained to end testing of inhibition of enzyme activity. To allow testing of anti-alglucosidase alfa IgG antibodies to be stopped earlier than 6 years.
10.1.3 Additional follow-up phase	Revised wording for study follow-up period duration specific for the UK and German patients.	To comply with the UK and German Health Authority position regarding the protocol language with regards to study follow-up period duration.
17.1 Appendix 1: Country-specific requirements	Revised wording for study follow-up period duration specific for the UK and German patients.	To comply with the UK and German Health Authority position regarding the protocol language with regards to study follow-up period duration.
17.2.6 Appendix 2: Protocol amendment history	Added new section.	To incorporate the changes from amended protocol 05 to amended protocol 06.

17.2.8 Amended protocol 08: 30 September 2020

This amended protocol (Amendment 08) is considered to be nonsubstantial based on the criteria set forth in Article 10(a) of Directive 2001/20/EC of the European Parliament and the Council of the European Union because it does not significantly impact either the safety or physical/mental integrity of participants or the scientific value of the study.

Overall Rationale for the Amendment

The overall rationale for this amendment is as follows:

- To comply with the Danish Medicines Agency (DKMA) position regarding the protocol language with regards to the study follow-up period duration.

Protocol amendment summary of changes table

Section # and Name	Description of Change	Brief Rationale
PROTOCOL AMENDMENT SUMMARY OF CHANGES TABLE	Document formatting revision	To update document history and provide overall rationale for the amendment
Clinical trial summary (Duration of study)	Revised wording for study follow-up period duration specific for patients in the UK, Germany and Denmark.	To comply with the DKMA position regarding the protocol language with regards to study follow-up period duration.
1.1 Graphical study design (Additional Follow-up Phase)	Revised wording for study follow-up period duration specific for patients in the UK, Germany and Denmark.	To comply with the DKMA position regarding the protocol language with regards to study follow-up period duration.
6.2.1 Duration of study participation for each patient	Revised wording for study follow-up period duration specific for patients in the UK, Germany and Denmark.	To comply with the DKMA position regarding the protocol language with regards to study follow-up period duration.
10.1.3 Additional follow-up phase	Revised wording for study follow-up period duration specific for patients in the UK, Germany and Denmark.	To comply with the DKMA position regarding the protocol language with regards to study follow-up period duration.
17.1 Appendix 1: Country-specific requirements	Revised wording for study follow-up period duration specific for patients in the UK, Germany and Denmark.	To comply with the DKMA position regarding the protocol language with regards to study follow-up period duration.
17.2.6 Appendix 2: Protocol amendment history	Correction to description of amended protocol 06 changes consistent with designation as a substantial amended protocol.	To correct typographical error
17.2.7 Appendix 2: Protocol amendment history	Added new section.	To incorporate the changes from amended protocol 06 to amended protocol 07.

Signature Page for VV-CLIN-0049122 v9.0

lts13769-16-1-1-amended-protocol09

Approve & eSign

Approve & eSign

NCT02032524

AMENDED CLINICAL TRIAL PROTOCOL 09 ERRATUM

COMPOUND: GZ402666 - avalglucosidase alfa (neoGAA, GZ402666)

An open-label, multicenter, multinational extension study of the long-term safety and pharmacokinetics of repeated biweekly infusions of avalglucosidase alfa (neoGAA, GZ402666) in patients with Pompe disease

STUDY NUMBER: LTS13769

STUDY NAME: NEO-EXT

Amended Clinical Trial Protocol 09	Version number: 1 (electronic 9.0)	Date: 21-Dec-2020
Version Number: 1	EudraCT IND Number(s) WHO universal trial number	2013-003321-28 109569 U1111-1147-3439
Date of Erratum: 25-Nov-2023	Total number of pages:	4

Any and all information presented in this document shall be treated as confidential and shall remain the exclusive property of Sanofi (or any of its affiliated companies). The use of such confidential information must be restricted to the recipient for the agreed purpose and must not be disclosed, published or otherwise communicated to any unauthorized persons, for any reason, in any form whatsoever without the prior written consent of Sanofi (or the concerned affiliated company); 'affiliated company' means any corporation, partnership or other entity which at the date of communication or afterwards (i) controls directly or indirectly Sanofi, (ii) is directly or indirectly controlled by Sanofi, with 'control' meaning direct or indirect ownership of more than 50% of the capital stock or the voting rights in such corporation, partnership or other entity

REASON FOR ERRATUM:

In the Clinical Trial Summary table (page 5) and in section 5.2 (page 33), exploratory efficacy variables are wrongly listed as secondary endpoints.

In the LTS13769 study protocol (Amended Clinical Trial Protocol 09, page 6), exploratory plasma and urine biomarkers and pharmacogenetics assessments are wrongly listed as secondary endpoints. These assessments are clearly exploratory in nature and are not reported in the Clinical Study Report, as also described in the study protocol:

- Amended Clinical Trial Protocol 09, page 50

9.3.4 Exploratory plasma and urine biomarkers

Fasted plasma and urine samples will be collected prior to IMP infusion for the assessment of exploratory biomarkers. Procedures for the collection, handling, and shipment of all samples will be included in the study-specific laboratory manual. Results will be used to inform on biomarker targets for future studies and will not be reported in the CSR.

- Amended Clinical Trial Protocol 09, page 51

9.5 Pharmacogenetic assessment

Fasted pharmacogenetic samples will be collected. Refer to the study-specific laboratory manual for guidelines on the collection and shipment of whole blood samples.

9.5.1 Skeletal muscle RNA expression analysis

In patients in whom the prior muscle biopsy, obtained in a prior avalglucosidase alfa study, had a glycogen content >5% or who show significant clinical decline, muscle tissue samples will be taken via biopsy of the lower extremity (quadriceps) muscle, as indicated in Section 9.3.2. An additional serum sample will be collected in connection with this analysis. These serum samples will be used to assess whether proteins for any of the mRNA targets that are identified in muscle are expressed in serum and therefore could be assessed as a serum-based marker of Pompe disease. Results will be used to inform on biomarker targets for future studies and will not be reported in the CSR.

9.5.2 Circulating microRNA analysis

Plasma samples will be collected and assessed for circulating microRNA concentrations on both the whole-genome and individual gene levels. Results will be used to inform on biomarker targets for future studies and will not be reported in the CSR.

DESCRIPTION OF CHANGE AND WHAT IS BEING CHANGED:

CLINICAL TRIAL SUMMARY

The following text on page 5:

STUDY OBJECTIVES	
Primary objective: To assess the long-term safety and pharmacokinetics (PK) of avalglucosidase alfa in patients with Pompe disease who have previously completed an avalglucosidase alfa study.
 
Secondary objective: To assess the long-term effect of avalglucosidase alfa on pharmacodynamic and exploratory efficacy variables to assess if the benefits of avalglucosidase alfa are maintained and to assess the time course of response.

-------------------------	---

Is replaced with:

STUDY OBJECTIVES	
Primary objective: To assess the long-term safety and pharmacokinetics (PK) of avalglucosidase alfa in patients with Pompe disease who have previously completed an avalglucosidase alfa study.
 
Secondary objective: To assess the long-term effect of avalglucosidase alfa on pharmacodynamic and exploratory efficacy variables to assess if the benefits of avalglucosidase alfa are maintained and to assess the time course of response.

-------------------------	---

The following text beginning on page 6:

SECONDARY AND EXPLORATORY ENDPOINTS	
Secondary endpoints:
 
Pharmacokinetics Estimates for C_{max}, AUC_{last}, AUC, $t_{1/2z}$, CL, and Vd.
 
Pharmacodynamics Skeletal muscle magnetic resonance imaging (MRI). Skeletal muscle needle or open biopsy. Urinary Hex4. Exploratory plasma and urine biomarkers.
 
Pharmacogenetics Serum skeletal muscle ribonucleic acid (RNA) expression analysis. Plasma circulating microRNA analyses.
 
Exploratory Endpoints:
 
Efficacy 6-minute walk test (6MWT). Pulmonary function testing (PFT) endpoints.

--	---

Is replaced with:

SECONDARY AND EXPLORATORY ENDPOINTS	Secondary endpoints: Pharmacokinetics Estimates for C _{max} , AUC _{last} , AUC, t _{1/2z} , CL, and Vd. Pharmacodynamics Skeletal muscle magnetic resonance imaging (MRI). Skeletal muscle needle or open biopsy. Urinary Hex4. Exploratory plasma and urine biomarkers. Pharmacogenetics Serum skeletal muscle ribonucleic acid (RNA) expression analysis. Plasma circulating microRNA analyses. Exploratory Endpoints: Efficacy 6-minute walk test (6MWT). Pulmonary function testing (PFT) endpoints. Pharmacodynamics Exploratory plasma and urine biomarkers. Pharmacogenetics Serum skeletal muscle ribonucleic acid (RNA) expression analysis. Plasma circulating microRNA analyses.
--	---

5.2 SECONDARY

The following text on page 33:

The secondary objective is to assess the long-term effect of avalglucosidase alfa on pharmacodynamic and exploratory efficacy variables to assess if the benefits of avalglucosidase alfa are maintained and to assess the time course of response.

Is replaced with:

The secondary objective is to assess the long-term effect of avalglucosidase alfa on pharmacodynamic ~~and exploratory efficacy~~ variables to assess if the benefits of avalglucosidase alfa are maintained and to assess the time course of response.

Signature Page for VV-CLIN-0658620 v1.0
lts13769-16-1-1-amended-protocol09-erratum-25-nov-2023

Approve & eSign

Approve & eSign

1 OVERVIEW AND INVESTIGATIONAL PLAN

1.1 STUDY DESIGN AND RANDOMIZATION

LTS13769 is an open-label, multicenter, and multinational extension study with repeated IV infusions of avalglucosidase alfa. Safety, pharmacokinetic, pharmacodynamic, pharmacogenetic, and exploratory efficacy data will be collected during this long-term study. The population will be patients with Pompe disease who have completed study avalglucosidase alfa TDR12857. Patients who received avalglucosidase alfa intravenous (IV) infusion 20 mg/kg of body weight every other week (qow) in the TDR12857 study will continue to receive the same dose in the extension study, while patients who previously received the 5 or 10 mg/kg qow dose will first continue on the same dose that they received in the TDR12857 study, and then provide consent to switch to the 20 mg/kg qow regimen for the remaining duration of the LTS13769 study (henceforth called the LTS-switch group in this document).

1.2 OBJECTIVES

1.2.1 Primary objectives

The primary objectives of the LTS13769 study are to assess the long-term safety and pharmacokinetics (PK) of avalglucosidase alfa in patients with Pompe disease who have previously completed an avalglucosidase alfa study.

1.2.2 Secondary objectives

The secondary objectives of the LTS13769 study are to assess if the benefits of avalglucosidase alfa are maintained and the time course of response, by examining the long-term effect of avalglucosidase alfa on pharmacodynamic (PD) and exploratory efficacy variables.

1.3 DETERMINATION OF SAMPLE SIZE

Sample size for the TDR12857 study was based upon empirical considerations. LTS13769 is the extension study of TDR12857; therefore, the number of patients in LTS13769 was determined by the subgroup of TDR12857 patients who consented to continue in the extension study. Thus, no formal sample size calculations have been performed for the TDR12857 or the LTS13769 study.

1.4 STUDY PLAN

The following diagram is a flowchart of the study: more detailed graphical design and study flow charts are presented in Section 1 of study protocol.

LTS 13769

1.5 MODIFICATIONS TO THE STATISTICAL SECTION OF THE PROTOCOL

The statistical section of the protocol was never changed in an amendment.

1.6 STATISTICAL MODIFICATIONS MADE IN THE STATISTICAL ANALYSIS PLAN

The following main modifications have been made in this version of SAP:

- Added Global Lung Initiative (GLI) 2012 reference equations to calculate FVC % predicted values
- Updated immunogenicity analysis. Some revisions of immunogenicity analysis are made to be consistent with integrated immunogenicity analysis plan.
- Added the second equations for calculating reference value for percentage of predicted total distance walked in 6MWT
- Added Algorithm-defined IARs to be consistent with integrated safety analysis plan
- Updated drug compliance definition to be consistent with COMET and mini-COMET studies
- Added K-M analysis for treatment-emergent adverse events
- The Appendix on Potentially Clinically Significant Abnormalities Criteria was updated

2 STATISTICAL AND ANALYTICAL PROCEDURES

The statistical analysis and reporting will be based on all data from study TDR12857 and its extension study, LTS13769. The baseline value is defined as the last non missing value prior to first TDR12857 treatment, unless otherwise specified. The rebaseline values will be the last non-missing assessment before patients switch to 20 mg/kg dose for LTS-switch patients.

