5 STUDY OBJECTIVES

5.1 PRIMARY

The primary objective is to assess the long-term safety and PK of avalglucosidase alfa in patients with Pompe disease who have previously completed an avalglucosidase alfa study.

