7 SELECTION OF PATIENTS

7.1 INCLUSION CRITERIA

- I 01. Patients with Pompe disease who previously completed an avalglucosidase alfa study.
- I 02. The patient and/or their parent/legal guardian is willing and able to provide signed informed consent, and the patient, if <18 years of age, is willing to provide assent if deemed able to do so.
- I 03. The patient (and patient's legal guardian if patient is <18 years of age) must have the ability to comply with the clinical protocol.
- I 04. The patient, if female and of childbearing potential, must have a negative pregnancy test (urine beta-human chorionic gonadotropin [β -HCG]) at baseline. Note: Sexually active female patients of childbearing potential and male patients are required to practice true abstinence in line with their preferred and usual lifestyle or to use two acceptable effective methods of contraception, a barrier method such as a condom or occlusive cap (diaphragm or cervical/vault cap) with spermicidal foam/gel/film/cream/suppository and an established non-barrier method such as oral, injected, or implanted hormonal methods, an intrauterine device, or intrauterine system for the entire duration of the treatment period.

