11.3 ANALYSIS POPULATIONS

- **Full Analysis Set:** This analysis set consists of all patients who received at least 1 complete infusion of IMP.
- **Safety Analysis Set:** This analysis set consists of all patients who received any amount of IMP and will be used as the basis for all safety analyses.
- **PK/Pharmacodynamics/Efficacy Analysis Set:** All patients without any critical deviations related to IMP administration, and for whom any PK/pharmacodynamic/efficacy data are available, will be included in the PK/pharmacodynamic/efficacy population.

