2.1.4 Safety endpoints

The safety analysis will be based on the reported adverse events (AEs) and other safety information, such as clinical laboratory data, vital signs, ECG, etc.

Observation period

The observation period will be divided into the following epochs:

- The screening epoch is defined as the study period preceding treatment, starting from the signed informed consent date (TDR12857) up to the first administration of IMP. (Note: medications known to have been taken by the patients within 28 days of the TDR12857 screening/baseline visit will be recorded in the CRF as well.)
- The treatment epoch is defined as the time from the start of the first administration of the IMP in the TDR12857 through the completion of the last administration of the IMP.
 - Before- and after-rebaseline periods within the treatment epoch will be used for select analyses
- The residual treatment epoch is defined as the time subsequent to the treatment epoch, from the completion of the last administration of the IMP through the last administration of the IMP + 28 days or the end of the protocol-defined follow-up period, whichever is earlier.

The treatment-emergent adverse event (TEAE) period will include both treatment and residual treatment epochs.

- The **posttreatment** epoch is defined as the period of time starting the day after the end of the treatment-emergent adverse event period up through the end of the study.

The on-study observation period is defined as the time from start of treatment in the TDR12857 until the end of the LTS13769 study (defined as the last follow-up visit as defined in LTS13769 protocol Section 10.1.2.9).

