2.2 DISPOSITION OF PATIENTS

This section describes patient disposition for both patient study status and the patient analysis populations.

Screened patients are defined as any patients who met the inclusion criteria and signed the informed consent. Patients who enrolled in the extension study, LTS13769, must have signed informed consent for the extension study, and met the additional inclusion/exclusion criteria, with one of the criteria being the completion of the TDR12857 study.

For patient study status, information in the following categories for either TDR12857 or LTS13769 will be presented in the clinical study report:

- Screened patients
- Screen failure patients
- Treated patients
- Completed TDR12857 study
- Patients who entered the LTS13769 study
- Completed LTS13769 study
- Patients who did not complete the study treatment (either in TDR12857 or LTS13769) by main reason

Number and percentage of patients treated in TDR12857 that fall into each category will be presented in a summary table. Percentages will not be calculated for the screened patients and screen failures. Reasons for treatment discontinuation will be supplied in table(s) giving numbers and percentages by study, dose, and patient groups.

A patient is considered lost to follow-up at the end of the study if he/she is not assessed at the last protocol planned visit and if the time from the last successful contact to the last protocol planned visit is greater than 30 days.

All critical or major deviations will be summarized in tables giving numbers and percentages of deviations by patient group.

Additionally, the analysis populations for safety, pharmacokinetics (PK), pharmacodynamics, and efficacy will be summarized by number of patients enrolled in the TDR12857 study:

- Full Analysis (FA) Set
- Safety Analysis Set
- PK/Pharmacodynamics/Efficacy Analysis Set

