2.3.2 Safety analysis set

The safety analysis set consists of all patients who received at least 1 complete infusion of IMP. It will be used as the basis for all safety analyses.

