2.4.5.1 Analyses of adverse events

Generalities

The primary focus of adverse event reporting will be on treatment-emergent adverse events. Pretreatment and posttreatment adverse events will be described separately.

If an adverse event date/time of onset (occurrence, worsening, or becoming serious) is incomplete, an imputation algorithm will be used to classify the adverse event as pretreatment, treatment-emergent, or posttreatment. The algorithm for imputing date/time of onset will be conservative and will classify an adverse event as treatment-emergent unless there is definitive information to determine it is pretreatment or posttreatment. Details on classification of adverse events with missing or partial onset dates are provided in [Section 2.5.3](#).

Adverse event incidence tables will present adverse events grouped by SOC and PT, including the number and percentage of patients experiencing AEs in each SOC/PT category and the associated event counts (see the paragraph below for sorting order). Multiple occurrences of the same event in the same patient will be counted only once in the tables within observation period presented

(pretreatment, treatment-emergent, and posttreatment). The denominator for computation of percentages is the safety population within each patient and dose group.

Sorting within tables ensures the same presentation for the set of all adverse events within the observation period (pretreatment, treatment-emergent, and posttreatment). For that purpose, the table of all treatment-emergent adverse events presented by SOC and PT sorted by the internationally agreed SOC order and decreasing frequency of PTs within SOCs will define the presentation order for all other tables unless otherwise specified. Sorting according to frequency of PTs will be based on the sum of patient counts for the patients in the 20mg/kg dose groups. In the case of the AE by maximal severity tables, the sum of patient counts for the severe AEs from patients in the 20 mg/kg dose groups will be used for the sorting of PTs.

For patients previously assigned to the 5 or 10 mg/kg dose groups in the TDR12857, entered the LTS13769 study, and switched to the 20 mg/kg dose group (LTS-switch group), additional AE summaries, as indicated in respective subsections below, will be generated for comparison of before- and after-rebaseline adverse events in these patients.

Analysis of all treatment-emergent adverse events

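### AE percentages pool everyone with a complete infusion since the first TDR12857 dose, and most AE tables do not show the LTS13769 entrants whom the primary objective names

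*SAP*

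**What the plan says.** **Population in the objective.** Protocol 5.1 sets the primary objective as "long-term safety and PK of avalglucosidase alfa in patients with Pompe disease who have previously completed an avalglucosidase alfa study". Criterion I 01 in Protocol 7.1 reads "Patients with Pompe disease who previously completed an avalglucosidase alfa study". SAP 1.1 also describes the study population as TDR12857 completers, and SAP 1.3 calls the LTS13769 patients a consenting subgroup of TDR12857.

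**Population in the analysis.**
- SAP 2 sets the data scope: "The statistical analysis and reporting will be based on all data from study TDR12857 and its extension study, LTS13769".
- SAP 2.1.4 starts the clock in the earlier study: "The treatment epoch is defined as the time from the start of the first administration of the IMP in the TDR12857".
- SAP 2.3.2: "The safety analysis set consists of all patients who received at least 1 complete infusion of IMP".
- SAP 2.4.5.1: "The denominator for computation of percentages is the safety population within each patient and dose group".
- SAP 2.2 says that the analysis populations "will be summarized by number of patients enrolled in the TDR12857 study".

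Keeping non-continuers is deliberate. SAP 2.4.2 presents medications for all TDR12857 enrollees, continuing or not, and the Appendix B footnotes set a window cutoff for patients who did not enroll in LTS13769.

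**Separations already planned.** SAP 2.4.5.1 plans before/after-rebaseline summaries for the LTS-switch group, for TEAEs and for serious TEAEs, each by SOC/PT, by relationship and by maximal severity. It also plans one Kaplan-Meier table of TEAEs by 6-month interval. SAP 2.4.5.3 allows a Kaplan-Meier analysis of liver-test elevations if necessary.

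**The concern.** Safety is the primary endpoint, and the question is long-term safety in patients who continued after a completed study. The main AE, SAE, IAR and AESI percentages answer a different question: whether an event was ever seen in anyone with one complete infusion since the first TDR12857 dose. A patient who left during or after TDR12857 has about half a year in which an event can be counted. One who reaches Month 72 of LTS13769 has about six and a half years. Both count as one patient in the denominator.

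The percentages also count a patient once for a given event over the whole treatment-emergent period. An event in the first weeks of TDR12857 therefore cannot be told apart from the same event recurring in year 5. From the main tables alone, a reader could not say how often a given event occurred in the extension among those who entered it. If the share who continued differs between groups, comparisons across groups are affected too.

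**Working it through.** The plan states no event rate, sample size or rollover figure, so there is no figure to reproduce. The check is on direction and possible size.

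**Formula.** Let f be the fraction of the safety set that never entered LTS13769, pc the event percentage in entrants and pn that in non-entrants. Then

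pooled % = (1 - f) × pc + f × pn.

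The pooled figure lies below pc only when pn < pc.

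**Inputs.** Follow-up comes from SAP Appendix B: target day 2372 for Month 72 of LTS13769 (2372/365.25 = 6.49 years), and target day 183 for the start of LTS13769 (0.50 years), used as approximate follow-up for non-entrants. The values of f and all event rates are assumptions.

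**(a) Events first arising in LTS13769.** Non-entrants cannot have them, so pn = 0 and pooled = (1 - f) × pc.

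| pc | f = 0 | f = 10% | f = 20% | f = 30% |
|---|---|---|---|---|
| 10% | 10% | 9% | 8% | 7% |
| 30% | 30% | 27% | 24% | 21% |
| 60% | 60% | 54% | 48% | 42% |

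**(b) Events accruing at a constant rate from the first TDR12857 dose,** with f = 20%, pc = 1 - exp(-rate × 6.49) and pn = 1 - exp(-rate × 0.50).

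| Rate per year | pc | pn | Pooled |
|---|---|---|---|
| 0.05 | 27.7% | 2.5% | 22.7% |
| 0.2 | 72.7% | 9.5% | 60.1% |
| 3 | about 100% | 77.8% | 95.6% |

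**(c) Events that cause early exit,** with assumed pc = 5% and pn = 25%.
- f = 10%: 0.9 × 5 + 0.1 × 25 = 7%
- f = 20%: 0.8 × 5 + 0.2 × 25 = 9%
- f = 30%: 0.7 × 5 + 0.3 × 25 = 11%

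Here pooling raises the figure, and restricting to entrants would remove events that matter.

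**What the planned separations cover.** The before/after-rebaseline split falls at the dose switch. SAP 1.1 has these patients first continuing their old dose in LTS13769, so the before period joins TDR12857 to early LTS13769. Patients on 20 mg/kg throughout have no split. The IAR and AESI tables carry no rebaseline summary. If the Kaplan-Meier table is of time to first TEAE of any kind, it allows for follow-up but may say little about late events: at the assumed 3 per year, 77.8% would already have had an event by day 183.

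**The case against.** The integrated approach is disclosed and defensible. Protocol 11.5 places the analysis baseline before the first dose in a prior study, and following everyone from first dose avoids selecting those who tolerated TDR12857. An entrants-only set makes exactly that selection and, if counted from the first LTS13769 infusion, drops early reactions. This stands. It is why new tables must not replace the integrated ones.

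A reader might infer that long-term percentages are diluted throughout. The documents do not support that: non-entrants contribute events as well as denominator, and case (c) runs the other way.

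A reader might also infer that no safety table is confined to LTS13769 patients. That is wrong for the LTS-switch TEAE and SAE tables, whose after-rebaseline counts are LTS13769 events in LTS13769 patients. By-visit laboratory and ECG summaries at LTS13769 visits also contain only entrants, because nobody else has data there. The gap is in the AE incidence tables.

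Part of the remedy is already planned. SAP 2.2 reports how many completed TDR12857 and how many entered LTS13769, with discontinuation reasons by study, dose and patient group. AE tables give event counts, SAP 2.4.3.1 shows exposure by duration category, and IAR listings give time from first infusion. A reader could recover overall rollover, but not AE percentages among entrants, from the summary tables.

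**Conclusion.** The mismatch between the objective's population and the AE denominator is in the text and does not depend on any assumption. For patients on 20 mg/kg throughout, and for all IAR and AESI tables, nothing planned presents AE incidence in the population that the objective names.

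The numerical effect is conditional. Events first arising in LTS13769 are reduced by exactly (1 - f), a relative loss of 10% to 30% if f is 10% to 30%, and none if everyone continued. Accruing events are reduced by less, and events that cause early exit may be raised. Neither f nor its variation across groups is in the documents, so no actual bias can be stated. Nor do the documents support calling the integrated analysis an error: it lacks a companion. The study is descriptive and the data will exist, so this is an inexpensive improvement that leaves the rest of the analysis intact.

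**What to change.** 1. Keep the integrated tables and label them as TDR12857 plus LTS13769.
2. Add to SAP 2.3 an LTS13769 safety set: patients who received any IMP in LTS13769.
3. For this set, present the TEAE overview and the SOC/PT, SAE, IAR and AESI tables, counting events from the first LTS13769 infusion. Place them beside the integrated tables, not in their stead.
4. Give exposure-adjusted rates with the new tables. Follow-up also differs among entrants, because participation runs 6 years and then, under Protocol 6.2.1, until approval, a country limit or withdrawal.
5. State the number not entering LTS13769 by group, extending the disposition table in SAP 2.2.
6. Align the safety-set definitions while editing SAP 2.3. SAP 2.3.2 requires one complete infusion, whereas Protocol 11.3 says "This analysis set consists of all patients who received any amount of IMP and will be used as the basis for all safety analyses".

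**Cost.** One added analysis set, a re-run of existing table shells and a short definition of exposure time; no new data. The downside is more tables in smaller groups. The entrants-only set selects patients who tolerated TDR12857, so a note should say that it is to be read with the integrated tables.
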